4.5.5 Study Discontinuation

The following data will be recorded, where available, for all enrolled patients at the time of discontinuing the study:

- Date of discontinuation
- Reason for discontinuation
- Updated assessments as outlined in Table 1, which depend on whether the patient is in the On-Treatment Follow-up or Post-Treatment Follow-up period
- Survival status

5. STATISTICAL METHODS

5.1 Sample size

The sample size for this study was chosen to provide better evaluation of the both serious and non-serious AESI, given the size of the current safety database. Evaluation of the sample size for the study was performed based on the expected rate of AESI in patients with relapsed or refractory CD30+ HL or relapsed or refractory sALCL treated with brentuximab vedotin to ensure sufficient enrolment in the study.

Table 2 shows the estimated 95% CIs for given frequencies of AESI from a study population of 500 patients which was calculated using an appropriate model for proportions, assuming a normal approximation to the binomial distribution. The targeted sample size of 500 (at least 50 of whom have a diagnosis of sALCL), provides an adequate level of precision to achieve the objectives of this study related to AESI, through estimating the proportion of patients with each individual AESI. The sample size of 500 includes the patients already being treated with brentuximab vedotin at the time of enrolment, the retrospective patients. It is assumed that approximately 15 to 20% (75 to 100 patients) of the study population will be retrospectively enrolled.

Confidential. Page 22 of 44

Table 2. Incidence Proportion and 95% Confidence Intervals for AESI

Proportion	Number of Events	95% Confidence Interval
0.00	0	(0.0%, 0.7%)
0.01	5	(0.0%, 2.0%)
0.02	10	(0.7%, 3.3%)
0.03	15	(1.4%, 4.6%)
0.04	20	(2.2%, 5.8%)
0.05	25	(3.0%, 7.0%)

5.2 Data Analyses

5.2.1 General Considerations

All SAEs and AESI (including both serious and non-serious AESI) verbatim terms will be recorded and coded using MedDRA. The severity of adverse events will be graded utilizing NCI CTCAE v4.03. All computations and generation of tables, listings and figures will be performed using SAS[®] version 9.2 or higher (SAS Institute, Cary, NC, USA). No formal hypothesis or statistical significance testing is planned. This approach follows the Guidelines for Good Pharmacoepidemiology Practices, Section D, point 10.

Details of the statistical analysis will be fully described in a written and approved statistical analysis plan (SAP). Descriptive analyses will be performed to gain an understanding of the qualitative and quantitative nature of the data collected and the characteristics of the sample studied. Descriptive statistics will be reported for all measured variables captured in this study. Summary statistics for continuous variables to be reported will include N, mean, median, standard deviation, 95% confidence interval (CI) and range. Skewed variables may be log-transformed or classed into quantiles of the distribution and analyzed as a categorical variable. Categorical variables will be reported using counts and proportions.

Analyses will be conducted on the entire enrolled population, including all patients exposed to brentuximab vedotin. In addition, analyses will be presented separately for patients prospectively and retrospectively enrolled to account for potential differences in the data reported, in particular the volume and nature of adverse events. Analyses by cohort will include disease history, ECOG performance status, and other background information to determine whether there are baseline differences between groups which could influence the safety results.

Because information collected is routinely recorded in medical records, it is expected that nearly all the data collected for the prospective cohort will also be available for the retrospective cohort. In addition, SAEs and the AESIs, in general, are events that should also be captured in patient records. However, to formally address the concern for completeness of

Confidential. Page 23 of 44

data for the retrospective cohort, where possible, the number and percentage of missing data items will also be tabulated and compared between the two cohorts.

Specific studies of brentuximab vedotin in elderly patients have not been conducted and clinical studies did not include sufficient numbers of patients aged 65 and over to determine whether they respond differently from younger patients. Therefore, where possible, relevant subgroup analyses will be performed by age group (i.e., < 65 years and \ge 65 years). Where appropriate, subgroup analysis may also be performed according to the following variables of interest: sex, CD30+ lymphoma type, ALK positivity (sALCL patients), long term treatment (i.e., > 16 cycles) and post-ASCT status. Additional subgrouping may also be applied as described in the SAP.

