4. STUDY DESIGN

4.1 Study Description

This is a multi-center international prospective, observational cohort study of patients who have been diagnosed with relapsed or refractory CD30+ HL or relapsed or refractory sALCL and are treated with brentuximab vedotin as part of routine clinical care. The study will target the enrolment of approximately 500 patients (at least 50 of whom have a diagnosis of sALCL), who are initiating or are currently being treated with brentuximab vedotin at approximately 75-100 sites in 12-15 countries in Europe and potentially in other countries outside of Europe. Patients already being treated with brentuximab vedotin at the time of enrolment will be considered to be retrospectively enrolled for purposes of analysis and inclusion in the PASS. The sample size for this study was based on the need for more information regarding the occurrence of both serious and non-serious AESI, relative to the

Confidential. Page 15 of 44

size of the current safety database. The study will continue for five years from the date of first patient enrolled. The study will be managed by the contract research organization (CRO) Quintiles, with oversight by Millennium Pharmaceuticals, Inc. (Millennium) project team.

Sites that treat patients with relapsed or refractory CD30+ lymphomas including HL and sALCL will be invited to participate in the study. Country and site selection will depend on the timing of commercial availability of brentuximab vedotin, reimbursement status, and physician product adoption rates in the selected countries to ensure that an adequate number of patients treated with brentuximab vedotin are available for enrolment into the study. The duration of the enrolment period may be extended (or contracted) based on actual patient accrual rates.

Eligible patients will be identified from sites where patients are initiating or already receiving therapy with brentuximab vedotin. No study specific visits or procedures will be required as part of patient participation in the study. Patients will be evaluated according to the physician's standard practice and discretion.

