4.2.1 Inclusion Criteria

To be eligible for enrolment, patients must meet all of the following criteria:

- Age at enrolment ≥ 18 years
- Clinical diagnosis (with histologic confirmation) of relapsed or refractory CD30+ HL or relapsed or refractory sALCL
- Patient is planned to start or is already receiving single agent therapy with brentuximab vedotin as part of routine clinical care

Confidential. Page 16 of 44

• Willing and able to provide informed consent

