4.3 Exposure Definition and Measures

This is an observational study of real-world treatment practices in this patient population. This protocol does not recommend the use of any specific treatments. No study medication is provided as part of participation.

Patients will be enrolled after the patient agrees to participate and signs the informed consent form. All exposure to brentuximab vedotin (including any exposure prior to enrolment) will be collected.

As an observational study to understand safety in patients treated in the post-marketing setting, no restrictions on concomitant treatments are associated with the study. All concomitant treatments (and subsequent treatments for lymphoma during follow-up) will be carefully recorded in order to evaluate their potential influence on the outcomes of interest.

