5.2.2 Planned analyses

5.2.2.1 Primary analyses

Serious Adverse Events (SAEs) and Adverse Events of Special Interest (AESI)

SAEs and AESI (including both serious and non-serious AESI) will be summarized by MedDRA system organ class (SOC) and preferred term (PT). Frequency and incidence proportion for all SAEs and AESI (as defined in Section 4.4.1) will be reported for patients who received at least one dose of brentuximab vedotin while on study.

The incidence rate and the associated 95% CI will be reported for SAEs and AESI.

Time at risk of SAEs and AESI will correspond to current/recent treatment with brentuximab vedotin. Current/recent treatment will be defined as time between the dates of first and last dose plus 30 days. All other follow-up time accrued for the patient will be considered occurring during past treatment with brentuximab vedotin; events reported during the past treatment period will be presented separately.

In addition, select events will be displayed by timing in relation to treatment start (e.g., by number of completed cycles) or time-to-event analysis may be carried out using Kaplan-Meier plots for the occurrence of the first reported occurrence of the adverse event, as appropriate for the event.

Identification and Description of Risk Factors for Peripheral Neuropathy

In addition, multivariable adjusted analysis will be performed to identify and describe risk factors for peripheral neuropathy (e.g., BMI, previous history of neuropathy, known toxic exposures) in the cohort. Risk factors for the first occurrence of new onset or worsening of peripheral neuropathy will be explored using a multivariable adjusted Cox regression model. Model assumptions concerning proportionality will be evaluated graphically in the usual manner. The inclusion of specific risk factors will be described in the SAP. A preliminary univariate analysis of the association of variables of interest with the outcome measure will be

Confidential. Page 24 of 44

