5.2.4 Limitations

As with all observational studies, one of the greatest concerns for external validity is selection bias. In order to minimise this source of bias, broad inclusion and exclusion criteria are to be applied and it is expected that most, if not all, patients indicated for treatment according to the product labeling (refer to SmPC in Appendix 2) will be eligible for enrolment in the study. In addition, sites will be instructed to invite consecutive eligible patients initially being prescribed who are planned to start or have already started treatment with single agent brentuximab vedotin as part of routine clinical care. Sites will be expected to complete a screening log which will collect a limited amount of data (e.g., age range, lymphoma type, disease stage, reason for not participating) for non-enrolled patients newly prescribed brentuximab vedotin in order to understand through descriptive analysis the representativeness of the enrolled population.

Confidential. Page 25 of 44

The risk of developing some of the AESI for this study, such as peripheral neuropathy, may be substantially affected by previous treatment regimens. The ability to assess the potential for confounding by previous exposures will be inherently limited by the completeness of the retrospective data available regarding lines of therapy. Similarly, the ability to evaluate potential risk factors for peripheral neuropathy will be limited by the availability of relevant medical history and exposure data across all patients.

Finally, the ability to meaningfully assess the safety of brentuximab vedotin in subgroups of interest, including the elderly and patients treated with more than 16 cycles of brentuximab vedotin, will be limited by the actual use of brentuximab vedotin in routine clinical care.

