7.2.1 Events to be recorded in the eCRF

All SAEs and both serious and non-serious AESI will be recorded in the eCRF, from the patient's first dose of brentuximab vedotin through 30 days after the patient's last dose of brentuximab vedotin. For retrospectively enrolled patients, this includes any SAEs or both serious and non-serious AESI identified in the medical record which occurred prior to study enrolment but after initiating the current regimen of brentuximab vedotin. From 31 days after the patient's last dose of brentuximab vedotin, only SAEs and both serious and non-serious AESI considered related to brentuximab vedotin will be recorded in the eCRF (see Table 3).

Documentation regarding an SAE or both serious and non-serious AESI, observed by the investigator or reported by the patient upon indirect questioning, should be made as to the

Confidential. Page 31 of 44

nature, date of onset, end date, severity, relationship to brentuximab vedotin, action(s) taken, and outcome.

If any of the same SAE or both serious and non-serious AESI, occur on several occasions in the same patient, then the event in question must be documented and assessed each time.

7.2.2 Events to be reported to Millennium Pharmacovigilance & Risk Management (PV&RM) or designee (in addition to being recorded in the eCRF)

All SAEs (regardless of relationship to brentuximab vedotin) and both serious and non-serious AESI considered related to brentuximab vedotin, occurring from the patient's first dose of brentuximab vedotin in the current regimen through 30 days after the patient's last dose of brentuximab vedotin, must also be reported to Millennium PV&RM or designee by faxing a completed SAE Form within one business day after becoming aware of the event (see Table 3). For retrospectively enrolled patients, this includes any SAEs (regardless of relationship to brentuximab vedotin) or AESI, both serious and non-serious, considered related to brentuximab vedotin identified in the medical record which occurred prior to study enrolment but after initiating the current regimen of brentuximab vedotin.

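### Retrospective patients must be alive and on treatment to enrol but are counted at risk from first dose, so pooled rates of fatal or treatment-ending events are biased downward

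*Protocol*

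**What the plan says.** Four provisions of the protocol combine.

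- **Who can enter.** Section 4.2.1 requires: "Patient is planned to start or is already receiving single agent therapy with brentuximab vedotin as part of routine clinical care". It also requires the patient to be "Willing and able to provide informed consent". Section 4.1 defines the retrospective group: "Patients already being treated with brentuximab vedotin at the time of enrolment will be considered to be retrospectively enrolled". A patient who died or stopped the drug before being approached fits neither route. Section 5.2.2.1 further restricts the reported frequencies to patients who had at least one dose while on study.
- **When time at risk starts.** Section 5.2.2.1: "Current/recent treatment will be defined as time between the dates of first and last dose plus 30 days". Section 4.3 adds: "All exposure to brentuximab vedotin (including any exposure prior to enrolment) will be collected".
- **Which events count.** For retrospective patients, section 7.2.1 includes events "identified in the medical record which occurred prior to study enrolment but after initiating the current regimen of brentuximab vedotin".
- **Who is analysed together.** Section 5.2.1: "Analyses will be conducted on the entire enrolled population, including all patients exposed to brentuximab vedotin". In addition, it presents prospective and retrospective patients separately and compares their baseline characteristics and missing data.

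On non-enrolled patients, section 4.2.3 asks for the reason, where obtainable, for every treated patient who was not enrolled. Section 5.2.4 describes the screening log more narrowly, as data "for non-enrolled patients newly prescribed brentuximab vedotin".

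**The concern.** This is immortal time, or left truncation that is not accounted for. A retrospective patient contributes the weeks between first dose and enrolment to the denominator, but is in the study only because nothing fatal or treatment-ending happened in those weeks. Patients to whom it did happen contribute neither an event nor person-time.

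The first objective is the occurrence of SAEs and AESI. The events affected are those grave enough to end treatment or life, and understating them is the unsafe direction for a post-authorisation safety study. They are not negligible: section 1 reports that 30% of patients in one phase 1 study discontinued because of adverse events. It also lists anaphylaxis among the notable related SAEs of the other phase 1 dose-escalation study.

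The synopsis leaves time at risk to the SAP, but section 5.2.2.1 already fixes it. An SAP that follows the protocol inherits the problem.

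**Working it through.** **The plan's own figure first.** Table 2 (section 5.1) gives 95% intervals for N = 500. It reproduces as p ± [1.96·√(p(1−p)/500) + 1/(2·500)], the normal approximation with continuity correction. At 5%: 1.96·√(0.05·0.95/500) + 0.001 = 0.0191 + 0.001 = 0.0201, giving 2.99% to 7.01% (printed 3.0% to 7.0%). The other non-zero rows also agree. The zero-event upper limit is the exact one, 0.74%. Retrospective patients: 0.15·500 = 75 and 0.20·500 = 100, as stated.

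**Inputs from the protocol.** Retrospective share f = 0.15 to 0.20 (section 5.1). Median exposure about 27 weeks in HL and 20 weeks in sALCL, and at most 16 cycles in the phase 2 studies, used as a 48-week cap (section 1; 3-week cycles). Tail of 30 days = 4.29 weeks (section 5.2.2.1).

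**Assumptions not in the protocol.** Candidate entry times uniform, averaging 6 to 18 weeks after first dose; 30% of treatment stops due to the event of interest; the shape of the hazard.

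**Steady-state benchmark.** Take exponential durations without a cap, and retrospective patients sampled at random while on drug. Their mean duration is doubled, with half of it before enrolment, so their rate is half the true rate. Their share of person-time is 2f/(1+f), so the pooled ratio is 1 − f/(1+f) = 1/(1+f): 1/1.15 = 0.870 and 1/1.20 = 0.833, an understatement of 13 to 17%.

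**One capped scenario in full** (constant hazard, median 27 weeks, f = 0.20, candidate entry averaging 18 weeks). Hazard of stopping: ln 2/27 = 0.02567 per week.

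- Prospective: event proportion 0.3·(1 − e^(−0.02567·48)) = 0.2125. Mean time at risk 0.7084/0.02567 + 4.29 = 31.88 weeks. Rate 0.00667 per week.
- Retrospective: from simulation, mean entry among those still on drug is 15.27 weeks and the event proportion is 0.166. Mean time on drug after entry is (0.166/0.3)/0.02567 = 21.55 weeks. From first dose: 15.27 + 21.55 + 4.29 = 41.11 weeks. Rate 0.00404, ratio 0.61.
- Pooled from first dose: (0.8·0.2125 + 0.2·0.166)/(0.8·31.88 + 0.2·41.11) = 0.2032/33.73 = 0.00602, ratio 0.90.
- Pooled with delayed entry: 0.2032/(0.8·31.88 + 0.2·25.84) = 0.2032/30.67 = 0.00663, ratio 0.99.

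**All scenarios** (simulation, 400,000 courses each; relative bias for a treatment-ending event, time counted from first dose):

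| Hazard | Pooled rate | Retrospective rate alone | Pooled proportion |
|---|---|---|---|
| Constant | −3% to −10% | −17% to −40% | −1% to −4% |
| Early-peaking (Weibull shape 0.5) | −7% to −17% | −42% to −64% | −5% to −10% |
| Rising with exposure (shape 2) | −0.2% to −3% | −1% to −14% | +1% to +3% |

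With delayed entry the pooled crude rate is 0.99 to 1.00 of the true rate under a constant hazard. Under the other two shapes it still differs by about −8% to +8%, because retrospective patients are then observed at a different stage of treatment.

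**The case against.** The strongest defence is that the protocol already shows the cohorts separately, so a prospective estimate free of this bias will be reported. That stands, and it is the main reason the point is not graver. But the separate display corrects neither the pooled rate nor the retrospective rate, and the precision argument in section 5.1 rests on the pooled 500. The baseline comparison, the missing-data counts and the reasons for non-enrolment describe selection without changing any risk set.

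A reader might infer several stronger things that the documents do not support:

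- **That 13 to 17% is the size to expect.** That is the uncapped steady-state benchmark. With treatment capped and earlier assumed entry, a constant hazard gives 3 to 10%.
- **That AESI in general are understated.** Section 1 describes the common phase 2 events as mainly mild to moderate and reversible, with neuropathy generally managed by dose delay and reduction. Events that end neither treatment nor life can occur before enrolment and are recorded. For neuropathy, described there as cumulative, the rising-hazard row is the relevant one: the rate barely moves and the proportion can rise slightly.
- **That the neuropathy Cox model is distorted.** Section 5.2.2.1 states neither its time origin nor its entry rule. Both may be left to the SAP, so no error can be attributed to the protocol here.
- **That the pooled figure is declared the primary estimate.** It is listed first, but section 5.2.1 does not rank it above the prospective one.

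**Conclusion.** The mechanism follows directly from the eligibility criteria and the stated time-at-risk rule. For fatal and treatment-ending events, the pooled and stand-alone retrospective incidence rates are biased downward; the pooled rate was low in every scenario examined. With 15 to 20% retrospective patients, the pooled understatement is about 3 to 10% under a constant hazard, up to 17% if events cluster early, and at most about 3% if the hazard rises with exposure. The retrospective rate shown alone is much more affected. Incidence proportions shift modestly and not always in the same direction.

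Confidence is high in the mechanism and in the direction for rates. It is lower in the size, which rests on assumed entry times and hazard shapes. The study is descriptive, without hypothesis tests, and an unaffected prospective estimate is planned. This should be fixed, but it does not invalidate the study.

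**What to change.** In section 5.2.2.1, for SAEs and AESI that end treatment or life:

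1. Take the headline incidence from the prospective cohort, or start retrospective patients' time at risk at enrolment (delayed entry) in pooled rates.
2. Wherever time since first dose is the axis, use left-truncated Kaplan-Meier or Cox methods, or give rates by cycle. Crude delayed-entry rates are unbiased only under a constant hazard.
3. Report retrospective patients' pre-enrolment events descriptively, so that none is lost.

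In section 5.2.4, name this bias, and reconcile the screening-log wording with section 4.2.3 so that both cover every treated patient who was not enrolled.

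The cost is some wording and one entry-time variable derived from dates already collected. If proportions rest on the 400 to 425 prospective patients, the half-width at 5% by Table 2's method rises from 2.0 points to 1.96·√(0.0475/425) + 1/850 = 2.2 points, or 1.96·√(0.0475/400) + 1/800 = 2.3 points. Limiting the change to events that end treatment or life keeps valid pre-enrolment information on all other events in the pooled rates.

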5.2.2 Planned analyses

5.2.2.1 Primary analyses

Serious Adverse Events (SAEs) and Adverse Events of Special Interest (AESI)

SAEs and AESI (including both serious and non-serious AESI) will be summarized by MedDRA system organ class (SOC) and preferred term (PT). Frequency and incidence proportion for all SAEs and AESI (as defined in Section 4.4.1) will be reported for patients who received at least one dose of brentuximab vedotin while on study.

The incidence rate and the associated 95% CI will be reported for SAEs and AESI.

Time at risk of SAEs and AESI will correspond to current/recent treatment with brentuximab vedotin. Current/recent treatment will be defined as time between the dates of first and last dose plus 30 days. All other follow-up time accrued for the patient will be considered occurring during past treatment with brentuximab vedotin; events reported during the past treatment period will be presented separately.

In addition, select events will be displayed by timing in relation to treatment start (e.g., by number of completed cycles) or time-to-event analysis may be carried out using Kaplan-Meier plots for the occurrence of the first reported occurrence of the adverse event, as appropriate for the event.

Identification and Description of Risk Factors for Peripheral Neuropathy

In addition, multivariable adjusted analysis will be performed to identify and describe risk factors for peripheral neuropathy (e.g., BMI, previous history of neuropathy, known toxic exposures) in the cohort. Risk factors for the first occurrence of new onset or worsening of peripheral neuropathy will be explored using a multivariable adjusted Cox regression model. Model assumptions concerning proportionality will be evaluated graphically in the usual manner. The inclusion of specific risk factors will be described in the SAP. A preliminary univariate analysis of the association of variables of interest with the outcome measure will be

Confidential. Page 24 of 44

performed. For the multivariable Cox regression, the number of variables included will be based on the number of outcome events. If any data reduction is required to reduce the pool of variables under consideration, an iterative process for variable selection will be conducted. Variables deemed of a priori importance for inclusion in multivariate models may be identified in discussion with clinical subject matter experts in order to compile a full set of potential covariates for selection in multivariate modeling.

Effect of Dose Modification

All brentuximab vedotin dose modifications including dose delays, temporary interruptions and permanent interruptions, and reported reason for change(s) from the start of brentuximab treatment will be summarised. The resolution of SAEs and AESI that require dose modification (e.g., dose decrease, discontinuation) will be explored. In addition, the occurrence of SAEs or AESI in patients for whom treatment is interrupted, modified or delayed will be explored.

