4.5.3 On-Treatment Follow-up

The following data will be recorded, where available, for all enrolled patients at each follow-up time point through 30 days after the last dose of brentuximab vedotin.:

- Visit date
- Current weight (kg)
- ECOG (if recorded)/Survival status
 - o Date and cause of death, if applicable
- New onset co-morbidities and updated medical history, including development of secondary malignancies, risk factors for neuropathy and status of neuropathy if ongoing at end of treatment with brentuximab vedotin
- Updated treatment status
 - o Brentuximab vedotin cycles
 - dose changes/discontinuations, change type, date (or duration) of change and reason for change
 - o Any newly initiated lines of therapy
 - o Radiation therapy

Confidential. Page 21 of 44

- Stem cell transplant (enrolling sites will be expected to continue to provide follow-up data in the event the patient temporarily transfers to another healthcare provider for the purpose of autologous or allogeneic SCT)
- Concomitant medications
- Relevant laboratory testing
- Occurrence of SAEs and both serious and non-serious AESI(per Section 7.2 Procedures for Recording and Reporting SAEs and AESI), since last follow-up

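### The current/recent-treatment window has no stop at the next lymphoma therapy, so for patients who switch within 30 days of last dose the next therapy's toxicity enters the brentuximab vedotin incidence

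*Protocol*

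**What the plan says.** Protocol section 5.2.2.1 ties the incidence of SAEs and AESI to one risk period: "Time at risk of SAEs and AESI will correspond to current/recent treatment with brentuximab vedotin". It then defines that period: "Current/recent treatment will be defined as time between the dates of first and last dose plus 30 days". What remains goes elsewhere: "All other follow-up time accrued for the patient will be considered occurring during past treatment with brentuximab vedotin", and events in that later period are shown separately. Time since the last dose is the only boundary named.

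Other sections show what can happen inside the period. Entry requires single-agent use (section 4.2.1), but after entry "no restrictions on concomitant treatments are associated with the study" (section 4.3). Section 4.5.3 lists the data recorded "at each follow-up time point through 30 days after the last dose of brentuximab vedotin". Among them are "Any newly initiated lines of therapy", radiation therapy and transplant: "Stem cell transplant (enrolling sites will be expected to continue to provide follow-up data".

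Section 7.1 defines AESI without regard to relationship to treatment, and Table 3 in section 7.2 collects every SAE and AESI to day 30 after the last dose. From day 31 only related ones are collected.

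Two statements point the other way. Section 4.3 says concomitant and subsequent lymphoma treatments are recorded so that their influence on the outcomes can be evaluated. The synopsis, under Interim and Final Analyses, leaves the definition of time at risk to the SAP.

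**The concern.** The first objective (section 3) concerns patients actively treated with brentuximab vedotin, and the split into current/recent and past treatment is meant to isolate that exposure. Take a patient who stops, starts salvage chemotherapy on day 10 after the last dose and has febrile neutropenia on day 25. That event counts as current/recent brentuximab vedotin in both the incidence proportion and the incidence rate. An infection during transplant conditioning begun on day 20 counts in the same way.

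Neutropenia, infections and neuropathy are the AESI most exposed to this. Patients who switch quickly contribute most of it, so differences between subgroups could partly reflect how soon the next therapy began. Section 4.3 promises to evaluate the influence of later treatments, but section 5.2.2.1 states no analysis that does so. The investigator's relatedness judgement does not help here, because the incidence is not restricted to related events.

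**Working it through.** The plan gives no figure for this point. Its only precision figure is Table 2, which reproduces and does not bear on the matter. For example, 5% of 500 with a continuity correction is 0.05 ± (1.96 × √(0.05 × 0.95/500) + 1/1000), or 2.99–7.01%, printed as 3.0–7.0%.

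**Inputs from the protocol (section 1, phase 2 studies):** dosing every 3 weeks, and median exposure of 27 weeks (9 cycles) in HL and 20 weeks (6 cycles) in sALCL.

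**Inputs assumed, because the documents give none:**
- f, the share of patients starting another lymphoma therapy within 30 days of last dose: 10–50%
- d, the day of that start after the last dose: 7–21
- k, the event rate on the next therapy relative to that on brentuximab vedotin: 3 or 10

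**Window for a median course,** W = (cycles − 1) × 21 + 30 days:
- HL: 8 × 21 + 30 = 198 days
- sALCL: 5 × 21 + 30 = 135 days

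The whole tail is 30/198 = 15.2% and 30/135 = 22.2% of the window. With the stated weeks instead, it is 30/(189 + 30) = 13.7% and 30/(140 + 30) = 17.6%. This is not the affected part, because only switchers' time after the switch is affected.

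**Affected share of person-time:** ov = f × (30 − d)/W.

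**Stated rate divided by the rate cut at the switch:** (1 − ov) + k × ov.

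| Course | f, d | ov | k = 3 | k = 10 |
|---|---|---|---|---|
| HL | 10%, day 21 | 0.1 × 9/198 = 0.45% | 1.01 | 1.04 |
| HL | 30%, day 14 | 0.3 × 16/198 = 2.42% | 1.05 | 1.22 |
| HL | 50%, day 7 | 0.5 × 23/198 = 5.81% | 1.12 | 1.52 |
| sALCL | 10%, day 21 | 0.1 × 9/135 = 0.67% | 1.01 | 1.06 |
| sALCL | 30%, day 14 | 0.3 × 16/135 = 3.56% | 1.07 | 1.32 |
| sALCL | 50%, day 7 | 0.5 × 23/135 = 8.52% | 1.17 | 1.77 |

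At k = 1 the ratio is 1.00 throughout.

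A narrower set (f = 10–30%, d = 10–20, windows of 219 and 170 days from the stated weeks) gives ov from 0.1 × 10/219 = 0.5% to 0.3 × 20/170 = 3.5%. At k = 3 the ratio is then 1.01–1.07.

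Incidence proportions move in the same direction: a patient whose first event follows the switch enters the numerator, while the denominator stays the same.

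**The case against.** Four objections deserve weight.

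- **The SAP may settle it.** The synopsis defers time at risk to the SAP, which is not at hand, and a censoring or sensitivity rule could sit there. This stands in part. However, section 5.2.2.1 does not defer: it fixes the period. The two statements need reconciling either way.
- **A 30-day all-cause window is a defensible choice.** It avoids discarding drug toxicity on a causal guess. With 3-weekly dosing, a switch on day 10 lies within one dosing interval, so a contribution from brentuximab vedotin cannot be excluded. Section 1 describes neuropathy as consistent with a cumulative effect. Cutting at the switch may also censor informatively if patients switch because of progression or toxicity. This stands, and it is why the cut analysis should sit beside the stated one and not replace it.
- **Relationship is assessed and later treatments are recorded** (sections 4.3 and 4.4.1). True, but neither supplies a rule that changes the incidence as section 5.2.2.1 defines it.
- **Listing an item for recording does not show that it is common.** This stands: section 4.5.3 shows that the protocol provides for next therapy inside the window, not how often it occurs.

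A reader might also infer that the window should close for any patient given another antineoplastic while brentuximab vedotin continues. The documents do not support that. Such patients are still being dosed, and classing them as past treatment would contradict the objective for actively treated patients.

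**Conclusion.** The point holds as a limited flaw in a fixed definition. Followed as written, section 5.2.2.1 counts some next-therapy toxicity as current/recent brentuximab vedotin. After the last dose this affects only patients who switch within 30 days; anything later is already shown apart. Other lymphoma therapy given between the first and last dose also falls inside the window.

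The size is unknown. Under the assumed ranges the rate ratio is about 1.01–1.17 at k = 3, and up to 1.77 at k = 10 for events much more frequent on conditioning or salvage therapy. All of this rests on assumed f, d and k, and on median courses standing in for total person-time.

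Two stronger readings are tempting and not supported. One takes the tail's 14–22% of the window as the contaminated share. Under the assumptions used here the affected share is 0.5–8.5%, and it is 0.5–3.5% in the narrower set. The other says the 21% neutropenia figure in section 1 would be reported as 25–42%. That comes from 0.21 + 0.79 × f × q, with 10% × 50% giving 24.9% and 30% × 90% giving 42.3%, where q is the share of switchers who become neutropenic. Both f and q are assumed. The upper end needs nearly all switchers to have a recordable event in the few days left, and section 7.1 does not count abnormal laboratory values as adverse events unless they prompt action or are judged clinically significant.

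**What to change.** In section 5.2.2.1:

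- Report SAE and AESI incidence proportions and rates twice: with the stated window, and with the tail after the last dose ended at the earlier of last dose plus 30 days and the day before the first new anti-lymphoma therapy, radiation or transplant conditioning.
- Show events between that start and day 30 on their own line, labelled as after start of other lymphoma therapy and within 30 days of last dose. Do not merge them with the past-treatment table, where only related events are collected.
- Where another antineoplastic is added while brentuximab vedotin continues, keep the person-time and events under current treatment and flag them separately.
- Confirm that the start date of the next therapy is recorded. Section 4.5.3 asks for dates of brentuximab vedotin changes but names none for new lines.
- Reconcile the synopsis deferral of time at risk to the SAP with the definition in section 5.2.2.1.

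The cost is one derived date, a sentence or two of text and one further table. Collection of events to day 30 is unchanged. The cut analysis has slightly less person-time, may be informatively censored, and loses late brentuximab vedotin effects after an early switch. Those effects remain in the uncut analysis beside it.
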